6.1.3 Handling of dropouts and missing data

Patients dropping out from the trial prior to study end will not be replaced. Data totally missing will not be estimated.

6.1.4 Subgroup analyses

No subgroup analyses are planned.

6.2 Method of statistical analysis

6.2.1 Primary objective

The primary objective is to compare dimensional bone changes from baseline (Visit 2) to three months (Visit 4) occurring in a single bound extraction site following ridge preservation using three different grafting materials and membrane, and one no graft membrane only group.

Assume the change is denoted C_A , C_B , C_C , and C_D , for group A, B, C, and D respectively. The null-hypothesis is then to test if:

$H_0: C_A = C_i$ ($i = B, C$, and D respectively)
can be rejected and hence
 $H_1: C_A \neq C_i$ ($i = B, C$, and D respectively)
accepted.

H_0 will be tested by means of the Wilcoxon rank sum test. A p-value less than 0.05 will be regarded statistically significant.

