OsteoGraf/N-300 is a xenoplastic bone grafting material that is a bovine-derived microporous hydroxyapatite.

Symbios OsteoShield Collagen Resorbable Membrane is a resorbable tissue matrix composed of Type-I Bovine collagen taken from the Achilles tendon. It presents as a multi-layer membrane which guides the healing of bone and the surrounding tissue, while the inner layers help prevent cellular and bacterial down growth into the site of bone preservation.

Duration of treatment

The study will be a 3 month follow-up. The treatment period includes tooth extraction followed by a ridge preservation procedure. Follow-up visits following the ridge preservation will occur at 14 days, and 3 months.

Outcome variables

Efficacy

Primary outcome variable:

- Volumetric osseous dimensional changes at 3 months

Secondary outcome variables:

- Horizontal and vertical dimensional changes in site (CBCT, cast measurements)
- Soft tissue dimensional changes (CBCT, cast measurements)

Patient reported outcomes

- Not applicable

Health economics

- Not applicable

Pharmacokinetics

- Not applicable

Safety

- Not applicable

Genetics

- Not applicable

Statistical methods

All primary and secondary outcome measurements will be analyzed by Wilcoxon rank sum test.

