1.2 Rationale

This study is intended to provide statistically robust evidence that Symbios demineralized Cortical cancellous mix, Symbios OsteoGraf LD-300, and OsteoGraf/N-300 combined with Symbios OsteoShield Collagen Resorbable Membrane can adequately support the alveolus during ridge augmentation

procedures, reducing the dimensional changes of both the alveolus and the overlying soft tissues. Additionally, a comparison between each material will be made, providing further evidence of each materials' ability to preserve the alveolus. An additional comparison of the use of the Symbios OsteoShield Collagen Resorbable Membrane with or without supportive graft material will be made. These comparisons are intended to define in objective terms the response of the hard and soft tissues to ridge augmentation using four different protocols currently used in clinical practice. To fulfill the goals of this project, the clinical study will enroll sufficient patients to perform statistical analyses of primary objectives.

A common and non invasive approach used for site assessment following a grafting procedure is the use of cone-beam computed tomography (CBCT) images (7). Several studies have demonstrated the reproducibility and accuracy of CBCT(8-11); concluding that there was no significant difference between the radiographic and clinical measurements. CBCT is now acknowledged by the American Academy of Oral and Maxillofacial Radiology, for the pre-surgical implant planning and augmentation procedures as the imaging modality of choice for preoperative cross-sectional images of potential implant sites (12). CBCT may be used to measure the alveolar bone condition prior to implant therapy and following ridge preservation. Therefore, when serial CBCT data is available, the direct volumetric assessment of ridge preservation outcomes will be possible.

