2 STUDY OBJECTIVES

2.1 Primary objective

The primary objective is to compare the volumetric changes in the osseous dimensions following a post-extraction ridge preservation procedure. Three different bone-grafting materials will be used, along with comparison to a non-grafted membrane only group. Data will primarily be obtained from DICOM images acquired by CBCT imaging. A surface based model will be constructed through image segmentation from both the pre- and post-operative CBCT images. The models will then be aligned/superimposed using a surface registration algorithm. Both images will be cropped to represent the same region of interest and the volumes will be calculated and compared.

Hypothesis: No significant differences in ridge volume maintenance are anticipated among the three grafting groups. The combined use of particulate graft material with a resorbable collagen membrane will maintain a greater ridge volume than the use of a resorbable collagen membrane alone.

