4.2.1.1.2 Derivation or calculation of variable

The changes in the bone volume between baseline (Visit 2) and 3 months (Visit 4) will be measured electronically using 3D analysis software. The change for each study site will be compared longitudinally and the average for each treatment group will be calculated and compared among treatment and control groups.

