4.2.2 Secondary Outcome Variables

4.2.2.1 Osseous dimensional changes

The amount of horizontal and vertical bone changes will be calculated using data from DICOM images acquired by CBCT using 3D software.

4.2.2.1.1 *Methods of assessment*

CBCT images will be obtained at baseline (Visit 2) and 3 months following alveolar ridge augmentation (Visit 4). Using 3D analysis software, the CBCT images will be aligned via superimposition through fiducial point registration, to permit evaluation of bone changes within the bound edentulous space.

4.2.2.1.2 *Derivation or calculation of variable*

The mid-alveolar point (middle of the extraction site) positioned on a tangent drawn from the mesial and distal adjacent tooth CEJs will be used as a reference point for assessment of dimensional bone changes in the Z-axis (Bone width) at 3, 6 and 9mm as measured from the height of the original buccal zenith (with the aid of a radiographic stent. Measurements will be taken from at these points from the buccal plate to the lingual plate. Changes in the Y-axis (bone height) will also be assessed. The changes in the bone dimensions between baseline (Visit 2) and 3 months (Visit 4) will be measured. The change for each study site will be compared longitudinally and the average for each treatment group will be calculated and compared among treatment groups.

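### The A-referenced test list in 6.2.1 (A-B, A-C, A-D) does not carry out the comparisons set by 1.2 and 2.1 on any reading: B-D, C-D, a pooled graft-versus-D test and B-C are all absent

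*Combined protocol and SAP*

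**What the plan says.** The aims are broad. In 2.1 the hypothesis is that particulate graft with a collagen membrane "will maintain a greater ridge volume than the use of a resorbable collagen membrane alone"; no single graft is named. The same paragraph says "No significant differences in ridge volume maintenance are anticipated among the three grafting groups". Section 1.2 describes the study as "intended to provide statistically robust evidence that Symbios demineralized Cortical cancellous mix, Symbios OsteoGraf LD-300, and OsteoGraf/N-300" (each with the membrane) can support the alveolus, promises a comparison between each material, and adds: "An additional comparison of the use of the Symbios OsteoShield Collagen Resorbable Membrane with or without supportive graft material will be made". In 4.2.1.1.2, "the average for each treatment group will be calculated and compared among treatment and control groups".

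The test is fixed in the synopsis: "All primary and secondary outcome measurements will be analyzed by Wilcoxon rank sum test".

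The formal hypotheses are narrower. Section 6.2.1 states "H_0: C_A = C_i$ ($i = B, C$, and D respectively", with a two-sided alternative and a 0.05 threshold, and 6.2.2 repeats this for the secondary outcomes. Section 6 lists no other contrast and gives no overall four-group test, testing order or multiplicity rule. Section 6.1 makes a separate SAP optional, and none is in the document. Section 6.3 sizes the trial on one difference, one SD, 0.05 and 80% power.

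**The concern.** Group D is the control in the 2.1 hypothesis, but it enters the formal list only once, against the allograft. Followed literally, the plan never tests the alloplast or the xenograft against membrane alone, never pools the grafts against it, and never compares alloplast with xenograft.

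An analyst would have to add tests to answer the trial's own question. The plan does not say which tests, or how they combine into a claim. If that is settled after results by group are known, the choice between pooled and per-graft analysis can follow the data. The choice matters, because the two approaches behave very differently depending on how many grafts work.

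**Working it through.** **1. Contrasts.** Four groups give 4 × 3 / 2 = 6 pairs. Each need is set against the list below.

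| Needed for | Contrasts | Listed in 6.2.1 |
|---|---|---|
| 2.1, per-graft reading | A-D, B-D, C-D | A-D only |
| 2.1, pooled reading | A+B+C versus D | none |
| 1.2, between materials | A-B, A-C, B-C | A-B, A-C |

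Every row is incomplete, so the list falls short on either reading of the graft-versus-membrane claim.

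**2. The plan's own sample size.** Section 6.3 gives a difference of 0.5 and an SD of 0.5, a standardised effect of 1.0. The normal formula gives 2 × (1.960 + 0.842)² / 1.0² = 15.7, so 16 per group. The t-test gives 16.7. Dividing by the Wilcoxon efficiency of 0.955 gives 17.5, so 18, which is the plan's figure. Allowing for dropout, 18 / 0.90 = 20. The 18 is therefore sound for one two-group Wilcoxon comparison at 0.05. Section 6.3 labels the outcome as horizontal bone change but uses mm³, so only the ratio 0.5/0.5 is used below.

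**3. What the listed tests can find.** These are simulated two-sided Wilcoxon tests on normal data with 18 per arm and a 1 SD effect. A continuity correction lowers most figures by about one point.

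- All grafts work: A-D has 81% power.
- B and C work, A equals D: A-D rejects about 5% of the time. B-D and C-D, both unlisted, would each have about 81% power.

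**4. False positives.** If all four groups are equal, three independent tests would give 1 − 0.95³ = 14.3%. The shared Group A lowers this to about 12–13%. If the grafts are equal and D is worse, as 2.1 expects, the chance of a false A-B or A-C difference is about 9%. A-D keeps its own 5% error.

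**5. Power under each way of defining the graft-versus-membrane claim (18 per arm, 1 SD).**

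| Claim | Three work | Two work | One works |
|---|---|---|---|
| Pooled A+B+C (54) versus D (18), one test at 0.05 | 94% | 62% | 18% |
| Per graft, any may be claimed, Holm: power per working graft | 74% | 69% | 65% |
| All three must succeed, each at 0.05 | 63% | – | – |

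At 20 per arm with all three working, the figures are 96% pooled, 79% per graft under Holm, 69% for all three, and 85% for A-D unadjusted. The Holm family error with all groups equal is 4.2%.

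**The case against.** The strongest reply is that the intent is clear and the test is fixed in advance. The synopsis names the Wilcoxon test for every outcome, and 4.2.1.1.2 leans towards group-by-group comparison with control. That stands, and the plan should not be described as having no prespecified analysis. But naming a two-group test does not say which groups are compared, and the one place that does say so leaves out what 2.1 needs. In the case where B and C work and A does not, A-B and A-C would probably show that B and C differ from A. That still does not compare them with membrane alone.

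Some stronger inferences are tempting, and the documents do not support them:

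- *That 1.2 and 2.1 require three separate graft-versus-membrane tests.* Section 1.2 announces one additional comparison in the singular, its sentence about the three products names no comparator, and 2.1 speaks of graft material generically. A pooled test is a fair reading. Because 1.2 joins the three products with "and", so is a claim that all three must succeed, which needs no adjustment.
- *That Group D must be the sole reference, with Holm.* The synopsis objective and 1.2 put the materials first. Formal A-B and A-C tests fit that emphasis and can stay.
- *That the plan claims equivalence of the grafts.* Section 2.1 only anticipates no significant differences. A non-significant result would not show sameness, but the plan does not say that it would.
- *That the listed tests inflate false graft-over-membrane claims.* In the scenario 2.1 expects, the extra risk falls on A-B and A-C.
- *That a large family error can be put on the secondary outcomes.* Widths are taken "at 3, 6 and 9mm as measured from the height of the original buccal zenith" and heights are added, but the plan does not count its secondary tests or give their correlations. The formal hypothesis in 6.2.2 describes only mid-buccal horizontal soft tissue.

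**Conclusion.** The concern holds in this form: the listed tests do not carry out 1.2 and 2.1, B-C is also missing, and neither the claim structure nor an error rule is stated. The contrast count comes from the text alone and needs no simulation.

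The practical size is clearest where B and C work and A does not: about 5% rejection for the one listed graft-versus-membrane test, against about 81% power for each unlisted one. The undefined choice matters as well. Pooled power runs from 94% down to 18% as the number of working grafts falls from three to one, while per-graft Holm power runs from 74% to 65%. These figures assume normal data, equal SDs, 18 evaluable per arm, and the 6.3 ratio at face value. It should be fixed, since the remedy uses data that the trial already collects. It does not show that the sample size of 18 is wrong for the single comparison it was built on.

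**What to change.** In 6.2.1 and 6.2.2, replace the A-referenced list with the graft-versus-D contrast or contrasts and all three graft-graft contrasts (A-B, A-C, B-C). Before any outcome is compared by group, state which graft-versus-membrane claim is intended:

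- (a) one pooled A+B+C versus D test at 0.05, with per-graft results supportive;
- (b) per graft, any of which may be claimed, with a named family rule such as Holm at 0.05; or
- (c) all three grafts must succeed, each at 0.05 without adjustment.

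The graft-graft tests may stay, reported with estimates and 95% confidence intervals. In 6.3, state that the 80% power applies to one two-group comparison at 0.05.

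**Cost.** There are no extra patients or measurements. Against 81% for A-D now, (a) gains power if all three grafts work but gives no product-by-product claim and is weak if only one works. Option (b) costs about 7 to 16 points per working graft (81 − 74 to 81 − 65). Option (c) has about 63% power for its joint claim.

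**Timing.** The document is dated October 4, 2016, and the synopsis estimated last completion in Q3 2016, so data collection may already have ended. If outcomes have already been compared by group, the added contrasts should be dated and labelled as specified late.

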6.2.2 Secondary objectives

Both the dimensional soft tissue changes from baseline (Visit 2) to three months (Visit 4) and linear soft tissue and osseous changes occurring in a single bound extraction site following ridge preservation using three different materials will be compared.

Assume the change (in the mid-buccal horizontal soft tissue dimensions from baseline to three months) is denoted C_A , C_B , C_C , and C_D , for group A, B, C, and D respectively. The null-hypothesis is then to test if:

$H_0: C_A = C_i$ ($i = B, C$, and D respectively)
can be rejected and hence
 $H_1: C_A \neq C_i$ ($i = B, C$, and D respectively)
accepted.

H_0 will be tested by means of the Wilcoxon rank sum test. A p-value less than 0.05 will be regarded statistically significant.

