4.2.2.2 Soft tissue dimensional change

The amount of soft tissue change will be assessed through the use of dental casts at two time points following extraction and ridge preservation, and 3 months.

4.2.2.2.1 *Methods of assessment*

Elastomeric impressions will be made of the site at baseline, and 3 months following extraction. The impression will be poured in dental stone, and the cast will be scanned using an optical/laser scanner to produce a digitized model. The digital models will then be aligned in 3D software and superimposed on one another and the relevant CBCT image utilizing the fiducial point registration algorithm.

4.2.2.2.2 *Derivation or calculation of variable*

The mid-alveolar point (middle of the extraction site) positioned on a tangent drawn from the mesial and distal adjacent tooth CEJs will be used as a reference point for assessment of dimensional bone changes in the Z-axis (soft tissue width) at 3, 6 and 9mm as measured from the height of the original buccal zenith and indicated on the radiographic stent. Measurements will be taken from at these points from the buccal contour to the underlying buccal plate. Changes in the Y-axis (soft tissue height) will also be assessed. The changes in the soft tissue dimensions between baseline (Visit 2) and 3 months (Visit 4) will be measured. The change for each study site will be compared longitudinally and the average for each treatment group will be calculated and compared among treatment groups.

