6 STATISTICAL METHODS AND DETERMINATION OF SAMPLE SIZE

6.1 Statistical evaluation – general aspects

A comprehensive Statistical Analysis Plan (SAP) may be prepared before database lock. If prepared, the SAP will be kept as an appendix to the Data Management Plan. When using the terminology descriptive statistics it means that number of patients, mean, median, standard deviation, minimum and maximum values will be presented for continuous data and frequencies and percentages for categorical data.

Descriptive statistics will be given for each variable in the study and p-values may be complemented by confidence intervals as appropriate. A p-value less than 0.05 will be considered “statistically significant”.

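### Section 6.2.2 allows up to 24 unadjusted secondary tests, each called significant at p<0.05: with no true differences, the chance of at least one false positive is about 65% for uncorrelated variables and about 28% at correlation 0.9

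*Combined protocol and SAP*

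**What the plan says.** **Variables.** Section 4.2.2.1.2 measures bone in the "Z-axis (Bone width) at 3, 6 and 9mm as measured from the height of the original buccal zenith" and adds: "Changes in the Y-axis (bone height) will also be assessed". Section 4.2.2.2.2 repeats the pattern for the other tissue ("soft tissue width) at 3, 6 and 9mm as measured from the height of the original buccal zenith"), again with a height. That is four bone and four soft-tissue changes.

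**Tests.** The synopsis, under Statistical methods, states: "All primary and secondary outcome measurements will be analyzed by Wilcoxon rank sum test". Section 6.2.2 sets a two-sided alternative for A against each of B, C and D. It describes the outcome as rejecting the null and accepting the alternative, and closes with "A p-value less than 0.05 will be regarded statistically significant". Section 6.1 sets the same threshold for the whole study ("A p-value less than 0.05 will be considered" statistically significant).

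**The written-out hypothesis.** The symbols in 6.2.2 are defined for one change, the mid-buccal horizontal soft-tissue dimension. The text does not call it a key secondary variable, does not limit the threshold to it, and does not say which of 3, 6 or 9 mm is meant.

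**What is absent.** There is no multiplicity adjustment, testing hierarchy or exploratory label. Section 6.1 makes a separate SAP optional, so no other document is committed to supply one.

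**The concern.** Section 6.2.2 uses confirmatory language for a set of tests whose joint error rate is not controlled. A plan followed to the letter could report one isolated p<0.05, for example bone width at one level for A against C, as a statistically significant difference between two commercial products. Section 1.2 says that the study is meant to provide statistically robust evidence and to compare the materials with one another, and section 3.2 says that the results should help clinicians choose between them. A chance result among the secondary variables would therefore be read as ranking the products.

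**Working it through.** **Inputs**
- Variables: 3 bone widths + 1 bone height + 3 soft-tissue widths + 1 soft-tissue height = 8 (4.2.2.1.2, 4.2.2.2.2). Each height is counted as a single measurement.
- Contrasts: A-B, A-C, A-D = 3, two-sided at 0.05 (6.2.2).
- Group size: 18 evaluable, 20 randomised (6.3).
- Correlation between variables (rho): not in the documents, so varied from 0 to 1.

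**The plan's own figure.** The documents state no error rate for the secondary family. The only related figure is the 18 per group in 6.3. With difference 0.5 and SD 0.5, the normal approximation gives 2 × (1.96 + 0.84)² × (0.5/0.5)² = 15.7, so 16 per group. A simulated exact Wilcoxon test on normal data has 78.1% power at 17 and 80.5% at 18. So 18 is reproduced, and 18/0.9 = 20. It is the size for one pairwise comparison at an unadjusted 0.05.

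**Number of tests.** 8 × 3 = 24. Expected false positives with no true differences: 24 × 0.05 = 1.2, whatever the correlation.

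**Chance of at least one false positive, all 24 tests**
1. Fully independent tests: 1 − 0.95^24 = 70.8%. This is too high, because the three contrasts share group A.
2. One variable, three contrasts sharing A: 12.5% by simulation (12-13% over runs), against 1 − 0.95³ = 14.3% if independent.
3. Eight uncorrelated variables: 1 − (1 − 0.125)^8 = 65.6%.
4. Eight equally correlated variables, simulated with normal statistics (200,000 runs) and with exact Wilcoxon tests (20,000 runs each):

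| rho | normal | Wilcoxon, n = 18 | Wilcoxon, n = 20 |
|---|---|---|---|
| 0 | 66% | 64% | 64% |
| 0.5 | 53% | 52% | 53% |
| 0.6 | 48% | 48% | 49% |
| 0.7 | 42% | 42% | 44% |
| 0.8 | 36% | 36% | 37% |
| 0.9 | 28% | 29% | 29% |
| 1.0 | 12-13% | 12% | 12% |

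The normal curve crosses 50% at rho of about 0.55.

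5. Correlation only within each tissue, none between tissues: 51% at within-tissue rho 0.70 and 49% at 0.75.
6. Widths highly correlated, height correlated 0.3 with them, tissues uncorrelated: 54% at width correlation 0.8, 50% at 0.9, 47% at 0.95.

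**Narrower readings of 6.2.2**
- The named soft-tissue variable at one level, three contrasts: about 13%.
- The same variable at all three levels, nine tests: 33% at rho 0 (1 − 0.875³ = 33.0%), 30% at 0.5, 24% at 0.8, 20% at 0.9.
- Only A-B and A-C on all eight variables, 16 tests: 53% at rho 0, 41% at 0.5, 27% at 0.8.

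**The case against.** Four arguments can be made for the plan.

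**The variables are correlated.** Widths at 3, 6 and 9 mm of the same socket may well move together. A reader might infer from the count of 24 that a false positive is more likely than not unless the measures are very highly correlated. The calculation does not support that. An equal correlation of about 0.55, or about 0.70-0.75 within tissue when the tissues are uncorrelated, already brings the chance below one half. Only the pattern in step 6 needs about 0.9. This limits the size of the problem but does not remove it.

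**One variable is named.** A reader might infer that no secondary variable is singled out. That is not accurate, because the hypothesis in 6.2.2 is written for the mid-buccal horizontal soft-tissue change. On the narrowest reading the family is three tests. But the synopsis extends testing to every secondary measurement, and 6.1 extends the threshold to the study. Even the narrowest reading gives about 13%.

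**The global null is not what the protocol expects.** For ridge volume, section 2.1 anticipates that graft plus membrane does better than membrane alone. If the linear measures follow, A-D is not a null comparison. This stands. But the same section anticipates no significant differences among the three grafts, and the 16 A-B and A-C tests alone still carry 27-53% for rho from 0.8 to 0.

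**Secondary outcomes are commonly read as supportive, and 6.1 allows confidence intervals.** True, but 6.1 makes intervals optional, and 6.2.2 uses reject-and-accept language instead of a supportive label.

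Two further inferences go too far. An unadjusted p<0.05 is weakened evidence, not an absence of evidence, and a very small p-value would survive adjustment. And the unspecified level leaves room for choosing among 3, 6 and 9 mm, but nothing in the plan provides for reporting only one of them.

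**Conclusion.** The concern holds as a multiplicity gap of uncertain size. Followed as written, the rule permits up to 24 unadjusted significance declarations on secondary variables. Under no true differences the chance of at least one false declaration is about 65% at zero correlation, about 50% near 0.55 and about 28% at 0.9. At no assumed correlation does it come down to the nominal 5%: even perfectly correlated variables leave 12-13%. The result rests on the 24-test reading of the synopsis with 6.2.2, on a global null, and on an assumed correlation structure. The named soft-tissue hypothesis does not close the gap, because it has neither special status nor a fixed level. The primary analysis is not affected by this point, and the matter should be settled before database lock.

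**What to change.** **Main change.** In 6.2.2, and consistently in 6.1 and the synopsis, limit the p<0.05 rule to the primary outcome. State that secondary variables are exploratory and are reported as group differences with 95% confidence intervals, without significance claims. Changing 6.2.2 alone would leave the general threshold in 6.1 and the synopsis instruction in force.

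**If a formal secondary claim is wanted.** Name one variable and one level in advance and control the error over its three contrasts, for example by Holm (ordered p-values against 0.05/3 = 0.0167, 0.05/2 = 0.025 and 0.05). Test any further level, or the other tissue, only in a pre-stated order that keeps the overall error at 0.05. Naming one level per tissue is not enough by itself: two variables × three contrasts leave six unadjusted tests, with error 1 − 0.875² = 23% if the tissues are uncorrelated.

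**Cost.** Wording only, with no change to data collection or sample size. The downside is that most secondary variables can no longer support a formal significance claim.
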